**The Effects of Mindfulness Meditation on Psychoneuroendocrinology in
Nursing Students**

Study Protocol

Date: July 30, 2019

NCT number: Not yet issued

Introduction

Stress has been recognized worldwide as a prevalent health issue in nursing education (1). Like nursing students in other countries, nursing students in Jordan have reported moderate to high levels of stress, sometimes higher than the levels reported by students from other disciplines (2, 3). Although acute stress works to sustain human hemostasis, repeated exposure to stress can influence students' health, academic performance, attrition, and ability to care for patients and themselves (4).

Previous studies have shown that stress can negatively impact the body. Specifically, the immune system can be negatively impacted by the activation of the hypothalamic-pituitary-adrenal (HPA) system (e.g. cortisol) (5). Because of stress, the hypothalamus releases a corticotrophin-releasing factor (CRF) that stimulates the release of adrenocorticotropic hormone (ACTH) from the anterior areas of the pituitary gland. ACTH stimulates the adrenal cortex to secrete cortisol, described as a stress hormone that mainly affects metabolic processes, and an elevated cortisol level suppresses the immune system and inflammatory functions (5). Further, an elevated cortisol level increases the release of pro-inflammatory factors such as C-reactive protein (CRP), which is the most widely used proinflammatory biomarker in clinical practice and which has been found to be associated with a variety of chronic illnesses such as major depression, coronary artery diseases, cancer, and diabetes mellitus (6, 7).

It has been reported that when dealing with stress, Jordanian nursing students mostly use inefficient, harmful coping methods such as avoidance and smoking. These methods have short-lived benefits but are harmful in the long run, resulting in a variety of physical and psychological health problems (8, 9). Therefore, nursing students in Jordan may need to learn to use more effective coping strategies.

There are several potentially beneficial stress-reduction methods which have been found to help students worldwide cope effectively with stress and its adverse health consequences (10). Mind-body therapies are being more widely used in Jordan, as they are easily accessible, easy to learn, and inexpensive (11). Specifically, mindfulness meditation is a mind-body therapy that has been gaining increasing attention in the recent literature and has demonstrated promising results across different populations and settings (12, 13). The target groups for mindfulness meditation include people with chronic physical pain, illnesses such as cancer, or mental illnesses, such as stress, anxiety, depression, or burnout (12). In addition, this mind-body therapy has been used among non-clinical populations, including students, therapists, and prisoners (14).

Whilst mindfulness meditation has been shown by a growing body of evidence to improve several health and psychological well-being measures in university students, its mechanism of action and how it improves stress and its related health responses remain debated in the literature. Garland et al. (2009) proposed a hypothetical causal model that argues for the role of mindfulness meditation in positive reappraisal coping, explaining that attending repeatedly in a mindful way evokes a transitory metacognitive state of mindfulness that remains for as long as that form of attention is sustained. With repeated practices, individuals, including students, can cultivate their predisposition to be mindful in daily life, which is known as trait mindfulness (15). Trait mindfulness is described as the cognitive ability to non-judgmentally observe sensations, thoughts, emotions, and the environment while simultaneously encouraging openness, curiosity, and acceptance (16). Previous studies among university students have supported this theoretical claim. A recent randomized controlled trial showed that four weekly sessions of mindfulness meditation improved trait mindfulness among university students and staff (N=561) (17), and another recent RCT

showed that three daily sessions of mindfulness meditation significantly improved state mindfulness among university students (N=40) (18).

Based on the mindful coping model (15), positive reappraisal is a cognitive coping strategy that enables people to adapt successfully to perceived stress, which is defined as the degree to which events are appraised as stressful and uncontrollable (19). For example, a student who perceives a given event or situation, such as an exam, as stressful (e.g. risk of threat, harm, or loss) and exceeding their abilities may practice mindfulness meditation to induce an adaptive response by decentering from this stress appraisal into a mode of mindfulness. In turn, this mode allows the student to pay attention to the dynamic process of consciousness itself rather than its contents, which enhances attentional flexibility and raises awareness. Based on this broadened, metacognitive awareness, the student can then reappraise the given event in a positive way by giving it a new meaning, which may evolve either through a conscious process of reflection or a more automatic process. The reappraisal of the event then leads to positive emotions such as compassion, trust, and confidence that ultimately decrease stress and its related physiological reactions, such as cortisol and CRP (15).

Previous studies have also supported the claims of this model regarding the effects of mindfulness meditation on perceived stress among university students. A previous RCT showed that 8 weeks of mindfulness meditation reduced study-related stress among university students (20). In addition to long-term interventions, RCTs using brief mindfulness meditation, with sessions ranging between 3 daily sessions to 4 weekly sessions, showed that these brief mindfulness meditation interventions decreased perceived stress among university students [21, 22, 23, 24].

In addition to its psychological effects, mindfulness meditation has been found to improve physiological indices of stress. It is hypothesized that mindfulness meditation

buffers stress reactivity, resulting in decreased cortisol responses and proinflammatory markers such as CRP. In a systematic review of 45 RCTs (25), the authors identified strong evidence of mindfulness meditation leading to reductions in serum cortisol and C-reactive protein. Similarly, another systematic review of RCTs concluded that mindfulness meditation has been found to reduce pro-inflammatory cytokines, including CRP, which is associated with the reduction of perceived stress and cortisol (26).

Although an increasing number of studies have demonstrated the effectiveness of mindfulness meditation in improving wellbeing and reducing stress among ill and healthy populations such as university students, these studies have been conducted only in western countries. Therefore, any generalization of these study findings to other populations of different cultures is limited due to these cultures' differing belief systems and self-care practices. Also, there have been in these previous studies variations in the operationalization and standardized delivery of mindfulness meditation, limiting the generalizability of the findings related to the distinct effects of this therapy on stress and health. In Jordan, there is a lack of evidence related to the effectiveness of mindfulness meditation on stress and its physiological indices in Jordanian people generally and nursing students specifically. Thus, this study aimed to examine the effects of a standardized version of mindfulness meditation on trait mindfulness, perceived stress, serum cortisol, and serum CRP in Jordanian nursing students.

The current study is the first to report findings related to the effects of mindfulness meditation on psychoneuroendocrinology among the target population. Practically, the findings of this study may guide nursing faculties in adopting mindfulness meditation in nursing colleges. Theoretically, the current study also extends the body of nursing knowledge and fills a gap in the literature regarding the effects of mindfulness meditation on psychoneuroendocrinology in nursing students outside the United States and Europe.

Methods

Design and Participants

The study used randomized controlled design (pre-posttest, two-group, randomized, blinded design). The study sample included undergraduate nursing students who were selected using convenience sampling from Jordan University of Science and Technology (JUST). Students were included if they were aged 18 years or over and taking a clinical course. Meanwhile, students were excluded if they were practicing any type of relaxation techniques or taking hypnotics, sedatives, anxiolytics, anti-depressants, or anti-hypertensive drugs.

Sample Size Calculation

G* Power software 3.1 was used to calculate the required sample size, given a MANOVA test, an alpha of .05, power of 0.95, number of dependent variables of 4, number of groups of 2, and effect size of 0.25 (18). A sample size of 80 was calculated, and an attrition rate of 35% was added based on a previous study with variables similar to those of the present study (27). Therefore, this resulted in a final total sample size of 108 participants.

Instruments

The study data were collected using self-reported and physical measures. For the self-reported variables, a self-report questionnaire was used. The first part of the questionnaire included questions related to the behaviors and demographic characteristics of the participants, including age, religion, gender, marital status, daily consumption of cigarettes, general health status, nutritional status, coping behaviors, and sleeping hours and quality. Meanwhile, the second part included scales used to measure trait mindfulness and perceived stress. As for the physical variables, the enzyme-linked immunosorbent assay (ELISA) procedure was used to measure serum biomarkers such as serum cortisol and serum CRP.

Trait Mindfulness. Trait mindfulness was measured using the Arabic version of the Mindful Attention Awareness Scale (MAAS) (28), which is a one-dimensional scale that includes 15 items measured on a six-point Likert-type scale ranging from 1 (almost always) to 6 (almost never). The total possible score ranges between 15 and 90, with higher scores indicating higher levels of trait mindfulness. The original scale has been shown to have strong psychometric properties when validated among college students (28). Further, the Arabic version of this scale has been shown to have excellent internal consistency and convergent validity for use among Arab populations (29). In the current study, the Cronbach's alpha for the Arabic version of the MAAS was .79, indicating good internal consistency.

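### The 35% attrition allowance was added to 80 (giving 108) instead of divided out (giving 124), so 0.95 power does not hold at the plan's own dropout rate

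*Combined protocol and SAP*

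**What the plan says.** Under Methods, Sample Size Calculation, the protocol describes one calculation: "G* Power software 3.1 was used to calculate the required sample size, given a MANOVA test", with "an alpha of .05, power of 0.95", four dependent variables, two groups and an effect size of 0.25. The type of effect size is not named.

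The allowance for dropout follows: "A sample size of 80 was calculated, and an attrition rate of 35% was added based on a previous study". The section ends: "Therefore, this resulted in a final total sample size of 108 participants".

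The Procedure section says that allocation to the groups was equal. The Statistical Analysis section names a one-way MANOVA as the test of the hypotheses. On missing data it says only that they were examined and handled as appropriate. The document has no replacement rule, no other stated enrolment target and no imputation plan that would restore the number available for analysis.

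**The concern.** An attrition rate is the proportion of enrolled participants who are lost. To end with a required number of completers, that number is divided by the proportion expected to stay. Here the required number was instead increased by 35% of itself. That gives too small a total, and the gap widens as the rate rises; at 35% it is large enough to matter.

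The section is the trial's only justification of its size. A reader will take it that 108 enrolled protects 0.95 power against the dropout the plan expects. If it does not, the chance of missing an effect of the assumed size is higher than the plan implies.

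**Working it through.** **Inputs** (from Sample Size Calculation unless noted)

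- Alpha 0.05, power 0.95, p = 4 dependent variables, 2 groups, effect size 0.25
- Required number before attrition: 80
- Attrition: 35%
- Stated total: 108
- Equal allocation (Procedure)

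**Step 1. Reproduce the base figure of 80.** For a two-group MANOVA the global test has an F distribution with p = 4 and N − p − 1 = N − 5 degrees of freedom. Taking 0.25 as f²(V), the noncentrality is λ = 0.25 × N.

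| N | df | λ | Power |
|---|---|---|---|
| 79 | 4, 74 | 19.75 | 0.949 |
| 80 | 4, 75 | 20.00 | 0.952 |

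The smallest N with power of at least 0.95 is 80, as the plan says. Other readings do not give 80:

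- λ = 0.25 × (N − 2) gives 82.
- Reading 0.25 as f, so that f² = 0.0625, gives 302.
- A univariate two-group ANOVA with f = 0.25 gives 210.

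**Step 2. Reproduce the stated total.** 80 × (1 + 0.35) = 80 × 1.35 = 108. The match is exact, so the method used is clear.

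**Step 3. Apply the plan's attrition to the plan's total.** 108 × (1 − 0.35) = 108 × 0.65 = 70.2, or about 70 completers. The shortfall is 80 − 70 = 10.

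**Step 4. Find the total that preserves 80.** 80 / (1 − 0.35) = 80 / 0.65 = 123.08. Rounded up to an even number for equal arms this is 124, or 62 per arm. Check: 124 × 0.65 = 80.6. The difference from the plan is 124 − 108 = 16 enrolled participants.

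**Step 5. Find the attrition that 108 can absorb.** 1 − 80/108 = 28/108 = 25.9%.

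**Step 6. Power by attrition with 108 enrolled** (same formula as Step 1, completers rounded down)

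| Attrition | Completers | Power |
|---|---|---|
| 25% | 81 | 0.955 |
| 30% | 75 | 0.937 |
| 35% | 70 | 0.917 |

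At 35% attrition the type II error is 1 − 0.917 = 0.083, against the planned 0.05. For 0.95 power with 70 completers, f²(V) would have to be 0.285 instead of 0.25.

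**The case against.** Several points can fairly be made for the plan.

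- **The effect is small.** Power falls by about 3.5 points, stays above 0.90, and falls that far only if attrition reaches the full 35%. Type I error, endpoints and analysis are unaffected. This stands, and it is why a correction of wording is enough.
- **The 0.95 belongs to the calculation that gives 80, and that calculation is right.** The section never says outright that 108 delivers 0.95 after a 35% loss. This is literally true. But the only purpose of an attrition allowance is to protect the required number, and the section calls the 35% an attrition rate taken from an earlier study. If it were only a margin, 108 would still not cover the rate that the plan cites.
- **The effect-size metric is not named, and the power figures assume a complete-case analysis.** Both stand as qualifications of the 0.917. Neither affects the gap between 70 and 80 completers.
- **Other counts may mean that 108 was not the actual size.** The Interventions section mentions 6 groups of 10 to 11 participants, and the Control Group section mentions subgroups of 10. If the 6 groups are all experimental, that arm is 60 to 66, equal allocation gives 120 to 132 in total, and a 35% loss leaves about 78 to 86. If they cover both arms, the total is only 60 to 66. Neither reading fits 108, and the text does not settle which is meant. The finding therefore concerns the stated target, which remains the only total the document gives.
- **The text is in the past tense and reports reliability coefficients from this study, so recruitment may be over.** That bears on whether 124 is still an option. It does not prevent correcting the statement.

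**Conclusion.** The concern holds. The required 80, the 35% attrition and the total of 108 are mutually inconsistent: at the plan's own rate about 70 participants remain. This rests on the plan's figures alone.

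The consequence for power is 0.917 instead of 0.95, a type II error of about 8% instead of 5%. That part assumes that 0.25 is f²(V), which the plan does not say but which returns exactly 80; that losses are equal in the two arms; and that the MANOVA uses completers only. The statement is wrong as written and should be corrected, but the error does not make the trial unsound.

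**What to change.** Correct the attrition sentence in Sample Size Calculation. Suggested wording:

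*The calculation requires 80 participants with complete data (MANOVA, f²(V) = 0.25, alpha 0.05, power 0.95). The total sample size is 108. If 35% are lost, about 70 will remain and power will be about 0.92. Power of 0.95 is kept only if no more than 28 of the 108 (25.9%) are lost.*

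The sponsor should confirm that f²(V) is the metric that was entered. The cost is wording only: the stated power becomes slightly less favourable, and recruitment, design and analysis do not change.

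If the sponsor prefers to keep 0.95 power at 35% attrition, and recruitment still allows it, the total is 124 (62 per arm), which is 16 more participants.

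In the same edit, it would help to reconcile the stated total with the subgroup counts in the Interventions and Control Group sections.

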In the current study, the ABC standardized version of mindfulness meditation was used, which includes 5 30-minute weekly sessions of mindfulness meditation and which has been found effective in improving stress and its responses (34). An additional 3-hour educational workshop about the intervention was provided before the actual training sessions to enhance the participants' understanding of the intervention. In the initial educational session, the principal investigator (PI) held a PowerPoint presentation for the participants in each experimental group, which included an explanation of the intervention rationale and procedures and a demonstration of the entire intervention protocol. The PI is an experienced practitioner who received stress-management training at the Psychology Department at Kent State University over 7 years ago and who has, since then, been practicing stress-management techniques, especially those used in the current study, on a daily basis. The participants were asked to briefly practice the intervention, and their performance was then evaluated by the PI to make sure that the intervention had been conducted correctly. The PI gave the participants the opportunity to ask questions during the educational session.

During the actual training sessions, the intervention was introduced to the participants in the experimental groups by the PI based on Smith's (2005) guidelines and protocols. The participants were divided into 6 groups, with 10 to 11 participants in each group. The

subgroups met separately in different classrooms, where the interventions were conducted, and provided with identical instructions. Each participant sat in a hard chair behind a desk. The classrooms had tiled floors, and the lights were dimmed during the relaxation phases and turned up when the participants were completing the study questionnaires. A trained research assistant with a master's degree in psychiatric health nursing randomly selected sessions to evaluate the delivery of the interventions using checklists produced according to Smith's protocols.

Smith's version of the mindfulness meditation intervention was used in the current study. The participants were asked to sit upright in a comfortable position, place their feet on the floor, and quietly observe and reflect on internal and external stimuli such as breathing, thought, feeling, physical sensation, and sound, without reactions, judgments, or evaluations. They were asked to quietly attend to, note, and let go of all internal and external stimuli. They were reminded that they should not try to think about, push away, or do anything with these stimuli, and that they should not focus on figuring out the connections between the stimuli. They were asked to simply let each stimulus come and go and wait for the next stimulus. Finally, the participants were told that they should not concern themselves with distractions and that if faced with a distraction, they should note it as yet another passing stimulus (e.g., "Ah, a distraction... how interesting") (34).

Control Group

Each of the control group subgroups had 10 participants. The participants were instructed to sit with their eyes closed and relax during the intervention sessions, in order to control for the nonspecific effects of trainer interaction, social interaction, attention, environment, time, and closed eyes (35). The timings of the control group interventions were similar to those of the experimental groups, whereby if a given experimental group

intervention lasted for 30 minutes, the control group participants would be asked to sit with their eyes closed and relax for 30 minutes also.

Procedure

First, approval from the institutional review board at JUST was obtained. After obtaining permission from the dean of the nursing college at JUST and the students' instructors, the PI visited the students in their classrooms. After the students' lecture had finished, the PI made an announcement explaining the study title and objectives and asked any students who were interested in participating to contact him either on the phone number assigned for the purposes of the study or via email. The PI arranged an initial meeting to meet with students who were interested in participating, which was to be held on another day in a private room at the university. At this meeting, the PI informed the students of the study objectives, risks, and benefits, in addition to answering the students' questions and assuring them that all collected data would be kept confidential. The students were also assured that they had the full right to refuse or discontinue participation at any time and that such refusal or discontinuation would not affect their academic achievement in any way. At the same meeting, informed consent was obtained from participants who agreed to participate and who met the eligibility criteria. After that, the participants were randomly assigned equally to the study groups using a computerized random numbers procedure carried out by a research assistant who was not involved in any other parts of the study. Finally, the dates and times of the sessions were determined.

In the 2-hour educational session, baseline measurements of the study variables were taken. Then, the PI delivered a PowerPoint presentation for the participants in each subgroup, as previously explained. At the end of the workshop, to avoid experimental contamination, the participants in each experimental group were asked not to share any information related to the intervention with the participants in the control group.

The actual training sessions were introduced to the participants in the experimental groups by the PI based on Smith's (2005) guidelines and protocols. Based on the ABC Relaxation Theory (Smith, 1999, 2002, 2005), at least two, and preferably five, weekly sessions of actual mind-body training should be provided to evoke relaxation and optimize health (36, 37). The sessions were held in a private, quiet, comfortable, and spacious room at the university. As previously mentioned, the dependent variables were measured twice, at baseline and at the end of the intervention (i.e., In the next morning after the 5th session).

Various strategies were followed to decrease measurement errors that could potentially be affected by variations in the data collection procedure. For example, filling out the questionnaire may be stressful for some subjects, hence influencing the objective measures. Therefore, the self-report measures were completed after the physical measures were taken. Also, all of the study measures in the intervention and control groups were taken in similar conditions, including similar room temperature and environment. In addition, quiet environments were maintained, with a "Do Not Disturb" sign placed on the doors of the rooms during the interventions and data collection. The data (questionnaire and blood samples) were collected by three research assistants with at least 10 years nursing experiences who were not involved in any other parts of the study.

Statistical Analysis

Statistical analysis was conducted using SPSS software (version 25). First, the data were examined for outliers, missing data, and violations of statistical tests assumptions and managed as appropriate. Descriptive statistics were used to describe the sample. The sample and study variables were described by measures of central tendency and dispersion appropriate to the level of measurement. Initial independent t-tests and Chi-squared tests were conducted to ensure that the randomization across the covariates was successful, and one-way MANOVA was used to test the study hypotheses. Post hoc one-way ANOVAs were

run to examine if there were significant differences in each of the dependent variables between the study groups. Due to multiple testing, the p-value was adjusted by dividing the p value of .05 by 4 (i.e., the number of dependent variables), with a level of .0125 considered as the level of significance for the ANOVA tests.

References

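### The planned total of 108, split equally, cannot be matched to the delivery groups the plan describes, and the number per arm is not stated

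*Combined protocol and SAP*

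**What the plan says.** Four sections of the combined protocol and SAP bear on the number of participants.

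- **Sample Size Calculation.** The inputs are "given a MANOVA test, an alpha of .05, power of 0.95", with "number of dependent variables of 4, number of groups of 2" and an effect size of 0.25. They give 80. A 35% attrition allowance is then added, and "this resulted in a final total sample size of 108 participants".
- **Procedure.** After consent, "the participants were randomly assigned equally to the study groups". With two arms, 108 means 54 in each.
- **Interventions.** Directly after a sentence about the experimental groups: "The participants were divided into 6 groups, with 10 to 11 participants in each group". The sentence does not say whether the six are the experimental groups or all groups in the trial.
- **Control Group.** "Each of the control group subgroups had 10 participants". The number of control subgroups is not given.

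The Statistical Analysis section says "one-way MANOVA was used to test the study hypotheses". No section gives a number per arm.

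**The concern.** The total, the allocation and the group sizes should agree, and they do not. An arm of 54 cannot be made from six groups of 10 or 11, and a control arm of 54 cannot be made from subgroups of 10. The six-group sentence can be read two ways, but neither reading recovers 108.

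What is at stake is whether the trial can be shown to reach its own requirement of 80 analysed. One reading puts the whole trial below 80 before anyone is lost. The other puts it above 108 and close to the target after the planned loss. A reader of the plan cannot tell which trial is being described.

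**Working it through.** **1. Reproduce the plan's figures.** The inputs are from the Sample Size Calculation section: alpha 0.05, power 0.95, p = 4 outcomes, k = 2 groups, effect size 0.25. The effect-size metric is not named. Reading it as f²(V) = 0.25 for the global MANOVA test:

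- df1 = p(k − 1) = 4
- df2 = N − k − p + 1 = N − 5
- noncentrality = 0.25 × N
- power = P(noncentral F > 95th percentile of the central F)

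The smallest N with power of at least 0.95 is 80 (power 0.952), which matches the plan. Reading 0.25 as f (f² = 0.0625) gives N = 302, which does not match. The attrition step is 80 × 1.35 = 108, which also matches.

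**2. Split 108 equally.** 108 / 2 = 54 per arm.

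- 54 / 6 = 9 per group and 108 / 6 = 18 per group; neither is 10 or 11.
- An experimental arm of 54 fits five groups of 10 to 11 (50 to 55), not six (60 to 66).
- 54 is not a multiple of 10, so control subgroups of 10 cannot make it up.

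**3. Build the totals from the group text.** Experimental groups hold 10 to 11 and control subgroups hold 10. The number of control subgroups is an assumption in every row.

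| Reading | Experimental | Control | Total |
|---|---|---|---|
| Six groups in all, three per arm | 30–33 | 30 | 60–63 |
| Six experimental, four control | 60–66 | 40 | 100–106 |
| Six experimental, five control | 60–66 | 50 | 110–116 |
| Six experimental, six control | 60–66 | 60 | 120–126 |

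No row contains 108. Over all mixes of such groups, only eight experimental with two control (88 + 20) and nine with one (98 + 10) reach 108. Neither has six groups or equal arms. If the arms must be strictly equal and each has the same number of groups, the only totals left are 60 and 120.

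**4. Power on the two readings with matching groups per arm, using the formula in step 1.**

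- Six groups in all, no loss: N = 60 gives 0.86 and N = 63 gives 0.88.
- Six groups in each arm: 120 × 0.65 = 78 and 126 × 0.65 = 81.9, about 82. Power is 0.9465 at 78 and 0.9574 at 82, so about 0.95.

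**5. Power if 108 stands.** 108 × 0.65 = 70.2, so about 70 completers. Power at N = 70 is 0.917, against the stated 0.95.

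**The case against.** The best defence is that 108 is a recruitment target from a calculation, while the group sentences, in the past tense, describe groups as formed for training. A target of 108 and a realised number near 120 can both be true, so none of the figures need be an error. This stands in part: the documents do not show which number is wrong, or that any one is. But they give no number randomised, and they allocate equally without saying how many, so the plan still cannot be reconciled from its own text.

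The context also favours the kinder reading. The six-group sentence follows one about the experimental groups, and control subgroup size is given separately. On that reading, with six control subgroups assumed, power after loss is about 0.95. This is fair, and it means no loss of power has been demonstrated.

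Some stronger conclusions are tempting but not supported:

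- **That the power calculation itself is contradicted.** The stated power rests on 80 analysed, and that figure reproduces. The group text conflicts with the recruitment total of 108 and its equal split.
- **That power falls to about 0.63 to 0.66.** This takes 35% off 60 to 63, leaving 39 to 41. It applies to one reading only. If the groups count attenders, some loss has already occurred and would be counted twice.
- **That totals could reach 66 or 132.** These need control groups of 11, which the Control Group section excludes.
- **That 124 were really randomised, because 80 / 0.65 rounds up to 124 and lies within 120 to 126.** The overlap is no evidence of what was done.

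Whether the analysis should allow for delivery in groups is a separate question and forms no part of this point. The planned one-way MANOVA does not use the group counts.

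**Conclusion.** The inconsistency holds: 108 allocated equally and the described delivery groups cannot describe the same set of people. Its effect on power is undetermined. It ranges from 0.86–0.88 with no loss (60 to 63 in total, 17 to 20 short of the 80 required) to about 0.95 after 35% loss (120 to 126 in total). The second figure assumes six control subgroups, a number the plan does not give. All power figures assume f²(V) = 0.25, which is inferred from its reproducing 80. Those after loss also assume that only completers are analysed.

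Whichever reading is right, the size statement needs correcting. If 108 is the true number randomised, the plan's own 35% loss leaves about 70 and power of about 0.92.

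**What to change.** Reconcile the Sample Size Calculation, Interventions, Control Group and Procedure sections:

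1. State one number randomised per arm.
2. State the number of subgroups in each arm and their sizes, so that they add up to that number.
3. Say whether the group sizes in the Interventions section count people randomised or people attending.
4. Replace 108 if the number randomised differs from it.
5. Restate power for the completers expected after 35% loss. If 108 stands, that is about 70 completers and power of about 0.92.

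The cost is protocol wording and one recalculation. No extra participants are asked for. The stated power may become less favourable.
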